5.11.6 Anaphylaxis

Anaphylaxis is defined by MedDRA SMQ “Anaphylactic reaction - Narrow” and will be listed.

- A by-subject listing of Anaphylaxis.

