### **5.2.4 Selected Adverse Events**

Additional data will be collected for the following selected AEs. The data should be recorded in the eCRF on the AE page and on the special form for that particular AE.

- Infections that require treatments with IV antibiotics, antifungals, or antivirals\*
- Opportunistic infections that require treatments with oral antibiotics, antifungals, or antivirals\*

- Injection-related reaction (IRR; an AE which occurs within 24 hours after study drug injection except where the event is not considered an allergic reaction)†

\* Selected AEs will be reviewed by Sponsor and Medical Monitor to identify infections requiring IV treatment and opportunistic infections that require treatments. AE listings will also be searched to identify any infections requiring IV treatment/opportunistic infections which have not been reported as Selected AEs.

† Each IRR will be reviewed by the Medical Monitor to assess the risk of anaphylaxis.

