#### **5.3.5.1 Diagnosis versus Signs and Symptoms**

##### *Injection-Related Reactions*

Injection-related reaction is defined as the event that occurs within 24 hours after study drug injection. An IRR should be recorded on the IRR page of the eCRF as "injection-related reaction", and individual signs and symptoms should also be captured on the IRR page of the eCRF.

But exceptive conditions are as follows:

- Anaphylaxis or anaphylactic shock:  
If the event is judged as anaphylaxis or anaphylactic shock by Investigator's discretion, it will be recorded on the Adverse Event page of the eCRF.
- Obviously not allergic reaction (e.g., infection):  
If the event is judged as not allergic reaction, it will be recorded on the Adverse Event page of the eCRF.

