## **6.6 SAFETY ANALYSES**

All safety analyses will be performed on the SAF. Safety variables to be assessed are AEs, AESIs, SAEs, selected AEs, injection site reactions, patient withdrawals due to AEs, change in 12-lead ECGs, measurements of laboratory parameters, and vital signs (including body weight).

Summary tables for number and percentage of patients with adverse drug reactions (i.e., AEs related to study drug) will be tabulated.

Adverse events will be summarized by System Organ Class and preferred term, based on Medical Dictionary for Regulatory Activities coding, and grade of severity. The incidence of treatment emergent AEs will also be displayed by severity and relationship to the study drug, respectively. In addition, the incidence of AEs leading to withdrawal from treatment and SAEs will be tabulated.

Incidence of Selected AEs (see Section 5.2.4) will be tabulated. IRRs will be further analyzed according to whether they meet Sampson's criteria for diagnosis of anaphylaxis (Sampson et al, 2006).

Laboratory values (including hematology, blood chemistry, and urinalysis), frequencies of laboratory abnormalities, vital signs (temperature, SBP, DBP and pulse rate), physical examination, 12-lead ECG, and suicidality (C-SSRS) will be summarized. Measurement and change from Baseline in continuous laboratory parameters (hematology, clinical chemistry, and urinalysis), continuous ECG, vital signs (blood pressures and pulse rate), and body weight will be summarized using descriptive statistics. When analyzing categorical data, the number and percentage of patients in each category will be presented. In addition, shift tables may be used to evaluate the number and percentage of patients having a different post-baseline status when compared to their baseline status. Numbers of patients who meet the marked abnormality criteria will also be presented.

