5.11.7 IRR and ISR

IRR in CRF selected AE (IRR) page will be summarized. ISR flagged as “Injection site reaction” in CRF selected AE (IRR) or general AE page will be summarized. The following summary tables will be provided:

- A summary of IRRs.
- A summary of ISRs by SOC and PT.
- A by-subject listing of all IRRs.
- A by-subject listing of all ISRs.

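### The SAP has no counterpart to the protocol's analysis of injection-related reactions by Sampson's criteria for anaphylaxis, and gives no reason for the omission

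*SAP*

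**What the plan says.** Protocol 6.6 (Safety Analyses) first asks for a tabulation of the selected adverse events, then adds that "IRRs will be further analyzed according to whether they meet Sampson's criteria for diagnosis of anaphylaxis". The paper that defines the criteria is in the protocol's reference list. The opening of Protocol Section 6 leaves detailed methodology to the SAP.

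Protocol 5.3.5.1 sets out how reactions are recorded. An event within 24 hours of an injection is entered on the IRR page under one generic term, and "individual signs and symptoms should also be captured on the IRR page of the eCRF". Two kinds of event go to the general Adverse Event page instead: those judged not to be allergic, and those already diagnosed. The second exception begins "If the event is judged as anaphylaxis or anaphylactic shock by Investigator's discretion". Protocol 5.2.4 adds a medical check: "Each IRR will be reviewed by the Medical Monitor to assess the risk of anaphylaxis".

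On the SAP side, 5.11.6 says that "Anaphylaxis is defined by MedDRA SMQ", using the narrow anaphylactic reaction query. The one output under it is a by-subject listing. SAP 5.11.7 says "IRR in CRF selected AE (IRR) page will be summarized" and provides a summary and a by-subject listing of IRRs, plus the same for injection site reactions. Sampson's criteria appear nowhere in the SAP: not in 5.11, not in the change log in Section 1, and not in the references in Section 6.

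**The concern.** A search of coded terms finds events according to the term under which they were recorded. A criteria-based classification asks whether the recorded findings, taken together, meet a definition. The two can disagree, and this protocol's recording rules show where. By design the IRR page holds reactions that the investigator did not diagnose as anaphylaxis, since diagnosed cases are sent to the other page. The Sampson step in Protocol 6.6 is the only analysis in either document that applies an anaphylaxis definition to that page.

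Protocol 5.1.1.7 treats anaphylaxis as a potential risk of any biologic, including this one, and states that none has been reported. A statement that no cases occurred is worth more when one stated case definition has been applied to every reaction in both groups. If the SAP is followed as written, the report will contain no such classification, and readers would have to judge each listed IRR for themselves.

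**Working it through.** No sample size, event rate or error rate enters this point, and the plan gives no figure to reproduce. The check is a comparison of texts.

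**1. Commitment against counterpart.** Protocol 6.6 names a method (Sampson's criteria) and the events to which it applies (IRRs). SAP 5.11.7 covers the same events but has no classification. SAP 5.11.6 covers anaphylaxis by a different method and is not restricted to IRRs. Neither section supplies what Protocol 6.6 describes. The SAP change log says that detail on identifying anaphylaxis and injection reactions was added; it mentions no analysis being left out.

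**2. Where each kind of event would appear.**

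| Event | Recorded on | SAP output | Under Protocol 6.6 |
|---|---|---|---|
| Diagnosed as anaphylaxis by the investigator | Adverse Event page | Open to the query in 5.11.6 | Already identified by diagnosis |
| Entered as an IRR, findings meet the criteria | IRR page, generic term | In the 5.11.7 summary and listing, not separated; in 5.11.6 only if an entry is coded to a term in the narrow query | Classified as meeting the criteria |
| Entered as an IRR, findings do not meet the criteria | IRR page, generic term | In the 5.11.7 summary and listing | Classified as not meeting the criteria |

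The second row is the gap. The SAP does not distinguish it from the third.

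**3. Whether the data exist.** Signs and symptoms are on the IRR page (Protocol 5.3.5.1). Vital signs are taken immediately before and at 15 and 60 minutes after an injection at injection visits (Protocol 4.5.1.7). There are three limits:
- An IRR may begin at any time within 24 hours, so the vital signs cover only the first hour.
- Doses given away from the site, which Protocol 4.3.2.2 allows in the extension, will have none.
- Table 7, as supplied, marks no vital signs for the four-weekly visits after Week 48.

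The eCRF is not supplied, so its fields for symptom timing cannot be confirmed.

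**4. Which protocol version.** SAP Section 2 cites Version 8.0 of 17 April 2017; the protocol supplied is Version 11. Version 11 states that substantive new text is in italics, and the Sampson sentence is not italicised, so it appears to predate Version 11. Nothing shows whether Version 8.0 contained it.

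**5. Size.** The documents give neither a count of IRRs, nor the terms in the narrow query, nor the text of the criteria. The number of events in the second row cannot be estimated.

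**The case against.** The strongest reply is that the SAP is silent rather than contrary. Its anaphylaxis section is about adverse events in general, while the protocol sentence is about IRRs, so the two need not be alternatives. The SAP also says it is to be read together with the protocol and never withdraws the Sampson analysis. That is fair. A reader might infer that the SAP has replaced the criteria with the query; the documents show only an unexplained omission.

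A reader might also infer that the SAP cannot use what is on the IRR page. That is not supported. IRRs are summarised and listed, and injection site reactions flagged on the same page are tabulated by preferred term, so some entries appear to be coded. Whether individual IRR symptoms are coded, and whether the query reaches them, is not stated. Even if it does, a search for single terms does not apply the criteria named in Protocol 6.6.

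Nor do the documents say that the Sampson step was meant to supersede the investigator's diagnosis. Protocol 5.3.5.1 keeps that diagnosis as a route of its own, and 6.6 presents the criteria as a further analysis.

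Finally, every IRR receives a second medical look. "Each IRR will be reviewed by the Medical Monitor to assess the risk of anaphylaxis" is a real safeguard for case handling. It does not fill the analytical gap, because the SAP defines no variable or table from that review. It is also true that Protocol 5.1.1 declares no important identified or potential risks for the drug, which limits the urgency but does not remove a commitment made in 6.6.

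**Conclusion.** The point holds as an omission that should be corrected. A safety analysis named in the current protocol has no counterpart in the SAP and no stated reason for its absence. The consequence is conditional: an IRR that meets the criteria but was not diagnosed as anaphylaxis may go uncounted in the SAP's anaphylaxis output, although it would still appear in the IRR listing.

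The conclusion rests on Protocol Version 11. It cannot be said that the SAP departed from the version to which it was written.

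No number of missed cases should be attached. With about 35 patients planned per group, a reader might compute 1/35 = 2.9 percentage points. That is the weight of one hypothetical case in the double-blind period. It says nothing about how likely such a case is.

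**What to change.** Add to SAP 5.11.7 a classification of each IRR as meeting or not meeting Sampson's criteria. State the inputs: signs, symptoms and timing from the IRR page, and post-dose vital signs where available. Say how a reaction is handled when vital signs are absent, since that will be usual for off-site doses. Report the result by treatment group for the double-blind period and overall for All SA237, the two safety populations in SAP 5.11. Keep the 5.11.6 query listing as a supplement.

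The double-blind period has ended and its results are known (Protocol 1.3). Those reactions should therefore be classified by reviewers who do not see treatment assignment, and the table should be marked as added later.

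If the sponsor no longer wants this analysis, the alternative is to amend Protocol 6.6 and give the reason.

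The cost is one classification rule, one table and some medical review. The main inputs are already collected, provided the IRR page holds usable symptom timing.

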5.11.7 IRR and ISR

IRR in CRF selected AE (IRR) page will be summarized. ISR flagged as “Injection site reaction” in CRF selected AE (IRR) or general AE page will be summarized. The following summary tables will be provided:

- A summary of IRRs.
- A summary of ISRs by SOC and PT.
- A by-subject listing of all IRRs.
- A by-subject listing of all ISRs.

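### SAP 5.11.7 takes injection-related reactions from the IRR page only, so anaphylaxis that Protocol 5.3.5.1 records on the Adverse Event page drops out of the IRR summary and listing

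*SAP*

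**What the plan says.** Three parts of the documents bear on this.

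- **Definition.** Protocol 5.2.4 makes the IRR a selected adverse event and describes it as "an AE which occurs within 24 hours after study drug injection except where the event is not considered an allergic reaction". The same section gives a recording rule for all selected AEs: "The data should be recorded in the eCRF on the AE page and on the special form for that particular AE".
- **Recording.** Protocol 5.3.5.1 gives the default for these reactions: "An IRR should be recorded on the IRR page of the eCRF". It then lists two exceptions. One is for events that are plainly not allergic. The other reads: "If the event is judged as anaphylaxis or anaphylactic shock by Investigator's discretion, it will be recorded on the Adverse Event page".
- **Analysis.** Protocol 6.6 promises "Incidence of Selected AEs (see Section 5.2.4) will be tabulated". It also promises a further analysis of IRRs by whether they meet published diagnostic criteria for anaphylaxis. SAP 5.11.7 says "IRR in CRF selected AE (IRR) page will be summarized", followed by a summary and a by-subject listing. For injection-site reactions the next sentence uses two sources: events so flagged "in CRF selected AE (IRR) or general AE page will be summarized". SAP 5.11.6 defines anaphylaxis by the narrow MedDRA SMQ and provides a by-subject listing only.

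**The concern.** The definition and the data source do not match. Protocol 5.2.4 excludes non-allergic events and nothing else, so anaphylaxis within 24 hours of an injection is an IRR. Protocol 5.3.5.1 moves that event to a page which the IRR analysis does not read. SAP 5.11.7 allows for two pages when it counts injection-site reactions, but not when it counts IRRs.

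Two outputs are affected. The first is the IRR incidence, which Protocol 6.6 requires because the IRR is a selected AE and which SAP 4.2.2 lists among the safety variables. The second is the anaphylaxis classification of IRRs in Protocol 6.6. The SAP does not specify that classification. If it were run on IRR-page records, it would leave out the very events that investigators had already judged to be anaphylaxis. Serious hypersensitivity is one of the risks that Protocol 5.1.1.7 singles out for management.

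**Working it through.** The documents give no IRR rate or expected count, so there is no figure to reproduce. The check sets the passages side by side and then gives a scale.

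**1. Is anaphylaxis within 24 hours an IRR?** By Protocol 5.2.4, yes. Its footnote has the Medical Monitor review each IRR for the risk of anaphylaxis, and Protocol 6.6 classifies IRRs by whether they are anaphylaxis. Both treat anaphylaxis as something found among IRRs. The two exceptions in Protocol 5.3.5.1 therefore differ in kind. The non-allergic exception repeats a limit already in the definition. The anaphylaxis exception changes only the page on which an event inside the definition is recorded.

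**2. Which page holds it?** Under the specific rule in Protocol 5.3.5.1, the Adverse Event page. Under the general rule in Protocol 5.2.4, the Adverse Event page and the special form. The two instructions differ.

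**3. Which outputs would include an event recorded only on the Adverse Event page?**

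| SAP output | Included? |
|---|---|
| 5.11.7 IRR summary and listing | No |
| Protocol 6.6 anaphylaxis classification, if run on IRR-page records | No |
| 5.11.2 AEs by SOC and PT, and by intensity | Yes |
| 5.11.3 SAE tables | Yes, if serious |
| 5.11.6 anaphylaxis listing | Yes, if coded to the narrow SMQ |
| 5.11.8 adolescent listings | Only if serious, through the SAE listing |

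The selected-AE outputs in SAP 5.11.4 are infection listings, so they do not supply the IRR incidence.

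**4. Scale.** Inputs: 35 patients per group (Protocol synopsis, Number of Patients). Assumptions: all 35 are treated, and the affected patient has no other event on the IRR page. A patient who does have one is already counted, and the incidence does not change.

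Fall in an arm's IRR incidence = omitted patients / 35:

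- 0 patients: 0
- 1 patient: 1/35 = 2.9 percentage points
- 2 patients: 2/35 = 5.7 points
- 3 patients: 3/35 = 8.6 points

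These counts are illustrative. Protocol 5.1.1.7 states that no anaphylaxis has been reported in satralizumab trials, so zero is a realistic value.

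**The case against.** The strongest reply is that the loss appears only when the definition is taken from one section and the recording rule from another. If Protocol 5.2.4 governs recording, the event is on both the Adverse Event page and the special form, and the IRR summary picks it up. If Protocol 5.3.5.1 governs, anaphylaxis may have been set apart from IRRs on purpose, and the SAP follows suit with separate sections 5.11.6 and 5.11.7.

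The first half stands in part. If sites completed both forms, nothing is missing. But Protocol 5.3.5.1 is the more specific instruction and names only the Adverse Event page, so the SAP cannot rely on double recording. The second half is weaker. A deliberate separation would have to appear in the definition, and Protocol 6.6 would have little reason to look for anaphylaxis among IRRs if anaphylaxis had been removed from them.

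Other parts of the reply stand in full. Adding Adverse Event page records without de-duplication could count an event twice. The SAP was written against protocol version 8.0, whereas the protocol reviewed is version 11. The recording rule is not marked as new text in version 11, but version 8.0 is not available to confirm that it was the same.

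**Conclusion.** Wrong as written, minor. Followed literally, SAP 5.11.7 leaves investigator-judged anaphylaxis within 24 hours of an injection out of the IRR summary and listing. It thereby understates the IRR incidence by up to 2.9 percentage points per omitted patient in an arm of 35, and possibly not at all. This rests on the 5.2.4 definition governing what an IRR is and on sites having followed the 5.3.5.1 page rule.

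A reader might infer more: that anaphylaxis goes unreported, that arms with and without a case would look alike, or that the IRR table loses its severe category. The documents do not support these readings. The events remain in the AE tables by treatment arm and, where the conditions in the table above are met, in the SAE tables and the anaphylaxis listing. SAP 5.11.7 specifies no severity breakdown for IRRs. Anaphylaxis is not one of the protocol's severity grades, which are mild, moderate and severe, and a severe IRR that is not judged to be anaphylaxis stays on the IRR page.

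**What to change.** In SAP 5.11.7:

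- Define the IRR analysis set as all IRR-page records plus Adverse Event page records of anaphylaxis or anaphylactic shock with onset within 24 hours after an injection. State how a missing onset time is handled.
- De-duplicate events found on both pages, and count each patient once in the incidence.
- Show the incidence by arm with and without the Adverse Event page records, so that the effect of the page rule is visible.
- Apply the anaphylaxis classification promised in Protocol 6.6 to the combined set.

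In the protocol, reconcile the recording instructions in 5.2.4 and 5.3.5.1 so that they name the same page or pages for anaphylaxis.

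The cost is a few sentences in the SAP and a merge of two existing eCRF pages by onset and injection time. No new data are needed. If the double-blind tables have already been produced, the combined set can be run as a supplementary table.

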5.11.8 Safety evaluations for the Adolescent population

The following analyses will be provided for the Adolescent population:

- A by-subject listing of all AESI.
- A by-subject listing of all SAE.
- A by-subject listing of all IRRs.
- A by-subject listing of all Infections.
- A by-subject listing of C-SSRS.

5.11.9 Clinical Laboratory Evaluation

For continuous laboratory measurements including hematology, clinical chemistry, and urinalysis, summary using descriptive statistics of the actual values and their change from baseline will be presented by treatment group at each visit. The laboratory tests to be performed are presented in Table 4-4.

When analyzing categorical data, the number and percentage of subjects in each category will be presented. In addition, shift tables may be used to evaluate the number and percentage of subjects having a different post-baseline status when compared to their baseline status.

A subject data listing will be provided for all laboratory data. Values outside the normal range will be flagged within the listing. A subject data listing will also be provided for all treatment emergent marked laboratory abnormalities (see Section 7.1).

The following summaries, listings and figures will be provided:

- A summary of each laboratory parameter in Table 4-4 and change from baseline will be provided by visit.
- A shift table based on the normal range for each laboratory parameter will be presented by double-blind period endpoint value relative to baseline by treatment group.
- A by-subject listing of laboratory parameters.

The summaries above will be provided by treatment group.

Table 4-4 Laboratory measurements

Hematology	Clinical chemistry	Urinalysis	Complement
Hematocrit	Calcium	Glucose	Complement tests (C3, C4 and CH50)
Hemoglobin	Phosphorus	Protein	
International normalized ratio	Serum electrolytes (sodium, potassium, chloride)	Urinary occult blood	
Platelet count	Ferritin	Urobilinogen	
Red blood cell (RBC) count	Albumin		
WBC count	Total serum protein		
Absolute differential count (neutrophils, eosinophils, lymphocytes, monocytes, basophils, other cells)	Blood urea nitrogen (BUN)		
	Creatinine		
	Uric acid		
	Alkaline phosphatase		
	AST		
	ALT		
	GGT		
	Total bilirubin		
	Fibrinogen		

	Lactate dehydrogenase (LDH) Total cholesterol Low density lipoprotein (LDL) cholesterol High density lipoprotein (HDL) cholesterol Triglycerides Creatine kinase (CK)		
--	--	--	--

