#### **5.1.1.2 Neutropenia and Potential Risk of Infection**

Reversible neutropenia was reported in 1 of 33 patients with RA in Phase 1 multiple dose study (SA-105JP).

*In the completed double-blind period of the Phase 3 studies, decreases in neutrophil counts have occurred following treatment with satralizumab, which was not associated with serious infections. The majority of neutrophil decreases were transient or intermittent.*

Neutropenia has been observed during administration of tocilizumab. Infections have been uncommonly reported in association with treatment-related neutropenia in long-term extension studies and postmarketing clinical experience.

Patients with a low neutrophil count  $<2 \times 10^3/\mu\text{L}$  will be excluded from this study.

Caution should be exercised in patients with a low neutrophil count and appropriate measures (such as interruption of satralizumab) should be considered if neutropenia persists.

Recommended dose interruption based on ANC results is shown in [Table 2](#).

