5.2 General Presentation Considerations

Unless otherwise specified, Week 0 (Day 1) visit, which in most cases should correspond to the date of first dose, will be the baseline in the double-blind period, in which the baseline measurements will be collected at Day 1 prior to the first injection.

The date of first SA237 dose will be the baseline in the All-Subjects-Treated (All SA237) population analyses, in which the baseline measurements will be collected on the day of the first dose, prior to the study drug injection.

The definition of each duration for analysis is as follows:

- Double blind period for efficacy analysis
 - Double-blind period starts on the day of the randomization. The double-blind period ends on the earliest day of 1) clinical cutoff date (CCOD), 2) the day before the first

treatment in the extension period, 3) the end of the study, or 4) last contact for patients lost to follow up.

- Double blind period for safety analysis
 - Double blind period starts on the day of first dose of study drug. The double-blind period ends on the same day as efficacy analysis..
- SA237 exposure duration for safety analysis (for All SA237 analysis)
 - SA237 exposure duration starts on the day of first dose of SA237. SA237 exposure duration ends on the earliest day of 1) CCOD, 2) the end of the study, or 3) last contact for patients lost to follow up.

The definition of summaries by visit is as follows:

- Summaries by visit for double blind period
 - Baseline is defined as the latest data before the date of first administration for all data. Summarized visits except for baseline are defined as follows. Irregular visits such as unscheduled visit between week X, dose outside the visit window (DOW), extra visit at relapsing, and the end of the study are out of scope. Week X visits are directly used for categories of time. In other words, time window is not applied. If there are the same visits data, one representative assessment nearest to the scheduled visit day will be summarized.
- Summaries by visit for All SA237 analysis

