 - Baseline is defined as the latest data before the date of first administration of SA237 for all data. Summarized visits except for baseline are defined as follows. Irregular visits such as unscheduled visit between week X, dose outside the visit window (DOW), extra visit at relapsing, and the end of the study are out of scope. Time window is applied as if visit schedules continue in the double blind period. Middle of each specified day of visit will be used for the range of time window of each visit. One representative assessment nearest to the specified day of visit in time window of each visit will be summarized.

Continuous data will be summarized in terms of the mean, standard deviation (SD), median, minimum, maximum and number of observations, unless otherwise stated. The minimum and maximum will be reported to the same number of decimal places as the raw data recorded in the database. The mean, median and SD will be reported to one more decimal place than the raw data recorded in the database. In general, the maximum number of decimal places reported shall be four for any summary statistics. If the data contains inequality signs, use the number on the end (i.e. treat " ≤ 0.02 " as "0.02") in analysis for calculation of representative value to be presented in the summaries.

For categorical parameters, the number and percentages of subjects in each category will be presented at the relevant time point. The denominator for percentage will be based on

the number of subjects appropriate for the purpose of analysis. Unless otherwise noted, percentages will be presented to one decimal place. Percentages will not be presented for zero counts and 100% will be presented as an integer. The denominator for all percentages will be the number of subjects in that treatment group within the population of interest, unless otherwise noted. Missing category will only be displayed when there are missing data.

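### The only listed laboratory shift table rests on one undefined endpoint value, and marked abnormalities are only listed, so neutrophil or platelet falls that recover are not counted by arm in any listed laboratory table

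*SAP*

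**What the plan says.** **Shift table.** The output list in SAP 5.11.9 has one shift table, on normal-range categories, which "will be presented by double-blind period endpoint value relative to baseline by treatment group". No section defines the endpoint value. A general sentence before the list says that "shift tables may be used to evaluate the number and percentage of subjects having a different post-baseline status when compared to their baseline status", but it is optional and does not say which post-baseline value is meant.

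**Marked abnormalities.** SAP 7.1 defines these in full: a value outside a set range plus a minimum change from baseline, on treatment or up to 30 days after it ends. Protocol 6.6 says: "Numbers of patients who meet the marked abnormality criteria will also be presented". SAP 5.11.9 says: "A subject data listing will also be provided for all treatment emergent marked laboratory abnormalities". Its output list has no count by arm.

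**By-visit summaries.** SAP 5.11.9 also states that "summary using descriptive statistics of the actual values and their change from baseline will be presented by treatment group at each visit". Under SAP 5.2, "Continuous data will be summarized in terms of the mean, standard deviation (SD), median, minimum, maximum and number of observations". The same section puts some visits out of scope for by-visit summaries: "Irregular visits such as unscheduled visit between week X, dose outside the visit window (DOW), extra visit at relapsing", and the end of the study.

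**Other safety measures.** SAP 5.11.4 classifies AST and ALT by the maximum post-baseline level. SAP 5.11.10 gives an incidence of treatment-emergent ECG abnormalities. SAP 5.11.11 gives the number and percentage of subjects with abnormal vital signs during the double-blind period.

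**Time course.** On neutrophils, Protocol 5.1.1.2 states: "The majority of neutrophil decreases were transient or intermittent". Protocol 5.1.1.3 reports platelet decreases but not their duration.

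**The concern.** Low neutrophils and low platelets each have their own risk section and action table in the protocol (Tables 2 and 3). The natural safety question is how many patients in each arm ever had a low count. A table with one value per patient, taken at the end of the period, does not answer it: a count that fell and recovered is classed as normal. The promised marked-abnormality count would answer it, because its definition accepts a qualifying result at any time on treatment. That count is missing from the SAP's outputs.

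The timing of the endpoint value adds to the problem. After an investigator-judged clinical relapse, study drug is withheld until extension entry (Protocol 4.5.3.2). The double-blind period for safety, however, runs to the day before the first extension dose (SAP 5.2). The withdrawal visit, which includes laboratory tests, is targeted at 12 weeks after the last dose (Protocol 4.5.2.3 and Appendix 1, Table 6). An endpoint value from these periods may describe a patient no longer being dosed.

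**Working it through.** The plan states no figure on this point, so the check is mainly a comparison of texts, followed by an illustration.

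**1. Which listed outputs count patients by arm for an abnormality at any time?**

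| Measure | Listed output | Counts a fall that recovered? |
|---|---|---|
| AST/ALT | maximum post-baseline category (SAP 5.11.4) | yes |
| ECG | incidence of treatment-emergent abnormality (SAP 5.11.10) | yes |
| Vital signs | subjects abnormal during the period (SAP 5.11.11) | yes |
| Neutrophils, platelets | shift to the endpoint value (SAP 5.11.9) | not on the natural reading |
| Neutrophils, platelets | by-visit statistics (SAP 5.11.9) | shows the minimum, not the number of patients |
| Neutrophils, platelets | marked abnormalities (SAP 5.11.9) | listed by subject, not counted by arm |

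**2. Do the adverse event tables fill the gap?** Under Protocol 5.3.5.4 a laboratory result becomes an adverse event if it has symptoms, changes study drug, leads to intervention or a change in concomitant therapy, or is judged clinically significant. Compare the thresholds:

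- Neutrophils: the marked-abnormality limit is 1.50 × 10⁹/L (1,500/µL), with a fall of at least 20%. Protocol Table 2 asks for no dose action above 1,000/µL.
- Platelets: the limit is 100 × 10⁹/L (100,000/µL), with a fall of at least 30%. Protocol Table 3 asks for no dose action above 75,000/µL.

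Neutrophils between 1,000 and 1,500/µL, or platelets between 75,000 and 100,000/µL, can therefore be a marked abnormality without triggering those tables. Such a result need not become an adverse event.

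**3. Timing of the endpoint value.** The withdrawal visit is targeted at 12 × 7 = 84 days after the last dose. The marked-abnormality window closes at 30 days. If the withdrawal visit supplies the endpoint, the shift table uses a value 84 − 30 = 54 days beyond the SAP's own window. The SAP does not say whether that visit, or the relapse visit, can supply it.

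**4. Illustration of the loss.** Inputs: laboratory tests at Weeks 2, 4 and 8 and every 4 weeks thereafter (Protocol Appendix 1, Table 6). Assumptions, none of them in the documents: one low value per affected patient, equally likely at each scheduled post-baseline visit, and the last scheduled visit used as endpoint. With m tests, the chance that the low value is the last is 1/m.

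| Last visit | m | 1/m |
|---|---|---|
| Week 24 | 7 | 14.3% |
| Week 48 | 13 | 7.7% |
| Week 72 | 19 | 5.3% |
| Week 96 | 25 | 4.0% |

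The result depends on the assumed number of low values. With k low values at random visits the chance is k/m: three give 3/7 = 43% at Week 24 and 3/13 = 23% at Week 48. If the low value lasts two consecutive visits, the chance that it is still present at the last visit is 1/(m − 1): 16.7%, 8.3% and 4.2% at Weeks 24, 48 and 96. A worst-value table captures every low value seen at a visit that it includes.

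**The case against.** The strongest reply is that transient falls are not hidden. By-visit statistics are given by arm and include the minimum, so a low count at a scheduled visit can show in that visit's range. A fall that leads to interruption or discontinuation of study drug is an adverse event by definition, and SAP 5.11.2 tabulates such events whenever they occurred. This stands. A reader might infer that transient falls will be absent from every arm comparison; the documents do not support that. What remains is that a visit minimum does not say how many patients were affected, the by-visit summaries leave out unscheduled and relapse visits, and step 2 shows that some marked abnormalities need not become adverse events.

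Further tempting readings also go too far:

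- **That the protocol calls both falls transient.** It says so of neutrophils only. The sentence reports completed double-blind results in protocol version 11, whereas the SAP is dated April 2018 and refers to version 8.0. It supports the concern but could not have guided the SAP.
- **That the table is known to use the last value.** This is the natural reading of an undefined term.
- **That the SAP deliberately dropped the marked-abnormality count.** The SAP is to be read together with the protocol and defines the criteria. The count is absent from the output list; nothing says it was withdrawn.
- **That rescue corticosteroids distort the relapse value.** Protocol 4.4.1 and 4.5.3.2 place rescue after the relapse assessment except in an emergency, so blood taken at that visit would ordinarily precede it.
- **That the loss falls mainly on the satralizumab arm.** The illustration applies equally to both arms. What shrinks is any absolute difference between them, in proportion to the capture rate.

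**Conclusion.** The concern holds in a limited form. As written, SAP 5.11.9 gives no by-arm number of patients who ever had a low neutrophil or platelet count in any listed laboratory table, and its outputs fall short of Protocol 6.6. AST/ALT, ECG and vital signs are treated differently in the same SAP. By-visit minima and adverse event tables lessen the gap without closing it.

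The omission of the count and the lack of a definition are plain from the text. The size of the loss is not: the capture rates of about 14%, 8% and 4% at Weeks 24, 48 and 96 rest on the single-low-value assumption and are illustrative. That the endpoint value may come after dosing has stopped is a possibility left open by the missing definition, not an established feature. The point concerns safety reporting and does not touch the primary efficacy analysis.

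**What to change.** 1. Base the by-arm shift tables on the worst post-baseline value in the double-blind period, lowest and highest separately and including unscheduled visits. Do this at least for neutrophils and platelets, on the same principle as the maximum used for AST/ALT.
2. If the endpoint table is kept, define the endpoint value: which visits can supply it, and whether values after the last dose count.
3. Add to the SAP 5.11.9 outputs the number of patients in each arm who meet the marked-abnormality criteria of SAP 7.1, as Protocol 6.6 states.
4. Optionally, count patients by arm according to the neutrophil and platelet categories of Protocol Tables 2 and 3. Neither document promises this.

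The scheduled laboratory data are already collected. The cost is SAP wording and extra table programming. Reported abnormality frequencies may look higher, because a worst-value table counts more patients than a single-value one.
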